# **Clinical Study Protocol**

## **Johnson & Johnson Vision Care, Inc.**

stratified by site and type of habitual lens wear (daily disposable and daily wear reusable). The ratio of habitual wearers of daily disposable lenses to habitual wearers of daily wear reusable lenses is 7:3 within each study site (7 habitual wearers of daily disposable lenses versus 3 habitual wearers of daily wear reusable lenses). See Table 1. The random scheme will be generated using the PROC PLAN procedure from Statistical Analysis System (SAS) Software Version 9.4 or higher (SAS Institute, Cary, NC).

Randomization will be performed at visit 1. The following must have occurred prior to randomization:

- Informed consent must have been obtained.
- The subject must have met all eligibility criteria.
- The subject's screening and baseline information must have been collected.

When dispensing test articles, the following steps should be followed to maintain randomization codes:

1. Investigator or designee (documented on the Delegation Log) will consult the lens fitting schedule to obtain the test article assignment for that subject prior to dispensing.
2. Investigator or designee will record the subject's number on the appropriate line of the lens fitting schedule.
3. Investigator or designee will pull the appropriate test articles from the study supply. All test articles that are opened, whether dispensed (placed/fit on eye or dispensed outside the clinical site) or not, must be recorded on the Test Article Accountability Log in the "Dispensed" section.

### **5.2. Masking**

This is a single-masked trial. The investigators may be aware of the study lenses based on a slight difference in lens color (the Test lenses will be slightly more turquoise in color than the Control lens).

Masking will be used to reduce potential bias. Subjects will be unaware of the identity of the investigational product. Investigators and clinical site personnel involved in the data collection will not be masked as to the identity of the investigational product.

### **5.3. Procedures for Maintaining and Breaking the Masking**

The identity of the study lenses will be masked to the subjects by over labeling the blister pack of the study lens. The label will contain the study number, lot number, sphere power, expiration date and the randomization codes.

The test articles mask shall not be broken unless information concerning the lens type is necessary for the urgent medical treatment of a subject. The Sponsor must be notified before the mask is broken.

# **Clinical Study Protocol**

## **Johnson & Johnson Vision Care, Inc.**

Under normal circumstances, the mask should not be broken until all subjects have completed the study and the database is finalized. Otherwise, the mask should be broken only if specific emergency treatment/course of action would be dictated by knowing the treatment status of the subject. In such cases, the investigator may, in an emergency, contact the medical monitor. In the event the mask is broken, the sponsor must be informed as soon as possible. The date, time, and reason for the unmasking must be documented in the subject record. The investigator is also advised not to reveal the study treatment assignment to the clinical site or sponsor personnel.

Subjects who have had their treatment assignment unmasked are expected to return for all remaining scheduled evaluations. Subjects who are discontinued will be replaced.

## **6. STUDY INTERVENTION**

### **6.1. Identity of Test Articles**

The following contact lenses will be used in this study:

Table 3: Test Articles

	Control	Test
Manufacturer	JJVC	JJVC
Name	AV OASYS 1-DAY	TRP-200
Hydration	PG	PG
Material	senofilcon A	senofilcon A
Packaging Form	Sterile blister pack	Sterile blister pack
Nominal Water Content (%)	38	38
Nominal Dk (edge corrected)	103	103
Nominal Modulus	101	101
Inversion Indicator	123	123
Nominal Base Curve/Diameter @ 22°C (mm)	8.5 / 14.3	8.5 / 14.3
Nominal Center [contact] D (mm)	0.085	0.085
Nominal Powers (D)	-1.00 to -6.00 in 0.25 steps	-1.00 to -6.00 in 0.25 steps
New UV/HEV-Filter	NA	Yes

At least 1080 lenses per SKU per study lens will be made available based on the following factors: sample size, bilateral wear, daily replacement, 2-week duration, safety margin of 2X, and US distribution model for the range of lenses -1.00 through -6.00 DS.

# **Clinical Study Protocol**

## **Johnson & Johnson Vision Care, Inc.**

### **6.2. Ancillary Supplies/Products**

The following solutions will be used in this study. Note that RevitaLens will be used primarily to transport potential problematic lenses back to the Sponsor.

Table 4: Ancillary Supplies

Solution				
Solution Name/Description	Acuvue™ RevitaLens Multipurpose Solution	Single use Eye-Cept® Rewetting Drops	LaciPure Saline Solution	ScleralFil Preservative Free Saline Solution
Manufacturer	Johnson & Johnson Vision	Optics Laboratory	Menicon	Bausch & Lomb
Preservative	alexidine dihydrochloride 0.00016% and polyquaternium-1 0.0003%	None	None	None

Lens cases and fluorescein strips (either 0.6 mg or 1.0 mg) will be supplied for use as needed.

### **6.3. Administration of Test Articles**

Test articles will be dispensed to subjects meeting all eligibility requirements, including any dispensing requirements set forth in this clinical protocol. Subjects will be dispensed an adequate supply of test articles to complete the study. Lost or damaged test articles may be replaced at the discretion of the investigator and/or the sponsor.

### **6.4. Packaging and Labeling**

The Test articles will be packaged in blisters as the primary packaging. The Test article will be over-labeled to mask the identity of the lens. The Test articles will be in plastic bags as the secondary packaging form. The sample study label is shown below:

# Clinical Study Protocol

## Johnson & Johnson Vision Care, Inc.

### 6.5. Storage Conditions

Test articles will be maintained at ambient temperatures at the clinical site. Test articles must be kept under secure conditions.

### 6.6. Collection and Storage of Samples

No samples will be collected as part of the study procedures.

When possible, any lens or test article associated with an Adverse Event and/or a Product Quality Complaint must be retained and stored in a glass vial with moderate solution pending directions from the sponsor for potential return to JJVC.

### 6.7. Accountability of Test Articles

JJVC will provide the Investigator with sufficient quantities of study articles and supplies to complete the investigation. The Investigator is asked to retain all lens shipment documentation for the test article accountability records.

Test articles must be kept in a locked storage cabinet, accessible only to those assigned by the Investigator for dispensing. The Investigator may delegate this activity to authorized study site personnel listed on the Site Delegation Log. All test articles must be accounted. This includes:

1. What was dispensed for the subject for trial fitting, to wear out of the office, or issued for the subject to replace appropriately between visits.
2. What was returned to the Investigator unused, including expired or malfunctioning product.
3. The number and reason for unplanned replacements.

The Investigator will collect all unused test articles from the subjects at the end of the subject's participation. Subject returned unused test articles must be separated from the clinical study inventory of un-dispensed test articles and must be labeled with the subject number and date

# Clinical Study Protocol

## Johnson & Johnson Vision Care, Inc.

of return. Following final reconciliation of test articles by the monitor, the Investigator or monitor will return all unused test articles to JJVC.

If there is a discrepancy between the shipment documents and the contents, contact the study monitor immediately.

## 7. STUDY EVALUATIONS

### 7.1. Time and Event Schedule

Table 5: Time and Events

Visit Information	Visit 1 Screening, Baseline, Treatment 1	Visit 2 2-week FU Treatment 1	Visit 2 Final Evaluation
Time Point		14 days after Visit 1 (+/- 1 day)	14 days after Visit 1 (+/- 1 day)
Estimated Visit Duration	2.0 hours	45 min	15 min
Statement of Informed Consent	x		
Demographics	x		
Medical History/Concomitant Medications	x	x	
Habitual Contact Lens Information	x		
Inclusion/Exclusion Criteria	x		
Study Questionnaires Baseline	x		
Entrance Visual Acuity	x	x	
Slit Lamp Biomicroscopy	x	x	x (if applicable)
Expanded Conjunctival Redness	x	x	x (if applicable)
Expanded Corneal Staining	x	x	x (if applicable)
Keratometry	x		x
Iris Color	x		
Subjective Spherocylindrical Refraction	x		x
Lens Selection	x		
Lens Insertion & Settling	x		
Visual Acuity and Over Refraction	x		
Lens Power Modification (if applicable)	x		

# Clinical Study Protocol

## Johnson & Johnson Vision Care, Inc.

Visit Information	Visit 1 Screening, Baseline, Treatment 1	Visit 2 2-week FU Treatment 1	Visit 2 Final Evaluation
Time Point		14 days after Visit 1 (+/- 1 day)	14 days after Visit 1 (+/- 1 day)
Estimated Visit Duration	2.0 hours	45 min	15 min
Subject Reported Ocular Symptoms	x	x	
Lens Fit Assessment	x	x	
Lens Wettability	x	x	
Surface characteristics		x	
Lens dispensing information and criteria	x		
Patient instructions	x		
Study Questionnaires FU		x	
logMAR Acuity		x	
Exit Acuity	x		x
Final Evaluation			x

### 7.2. Detailed Study Procedures

#### VISIT 1

The subjects must enter the visit wearing their habitual contact lenses.

Visit 1: Screening			
Step	Procedure	Details	
1.1	Statement of Informed Consent	Each subject must read, understand, and sign the Statement of Informed Consent before being enrolled into the study. The Principal Investigator or his/her designee conducting the informed consent discussion must also sign the consent form.  Note: The subject must be provided a signed copy of this document.	
1.2	Demographics	Record the subject's year of birth, age, gender, race and ethnicity.	
1.3	Medical History and Concomitant Medications	Record the subject's medical history and concomitant medications.	
1.4	Habitual Lenses	Record the subject's habitual lens type, parameters, lens care solution, wear modality and approximate prescription date.	

**Clinical Study Protocol**  
**Johnson & Johnson Vision Care, Inc.**

Visit 1: Screening			
Step	Procedure	Details	
1.5	Habitual Wear Time	Record the average wearing time and comfortable wearing time.	
1.6	SCL Rx Confirmation	
The investigator confirms:
 
 
1. The subject is wearing a SCL Rx that has been confirmed current (up-to-date) within the prior 6 months.
 
2. The subject has worn the up-to-date SCL Rx for at least 2 weeks.
 
	
1.7	Eligibility after Screening	
All responses to Screening Inclusion Criteria questions must be answered “yes” and all responses to Exclusion Criteria must be answered “no” for the subject to be considered eligible.
 
If subject is deemed to be ineligible after screening, proceed to Final Evaluation and complete Subject Disposition. Refraction and Biomicroscopy forms do not need to be completed as part of Final Evaluation.
	

Visit 1: Baseline			
Step	Procedure	Details	
1.8	Baseline Questionnaire	
The subject will respond to the following Baseline Questionnaires based on their habitual lenses:
 
 
1. CLUE Baseline
 
	
1.9	Entrance Visual Acuity	Record the distance Snellen visual acuity (OD, OS, and OU) to the nearest letter with their habitual contact lens correction in place. Subjects must read the smallest line until at least 50% of the letters are read incorrectly.	
1.10	Remove Habitual Lens	The subject’s habitual lenses will be removed and stored in their own lens case. If they forgot to bring their lens case, one will be provided to them.	

**Clinical Study Protocol**  
**Johnson & Johnson Vision Care, Inc.**

Visit 1: Baseline		
Step	Procedure	Details
1.11	Slit Lamp Biomicroscopy	
FDA Slit Lamp Classification Scale will be used to grade the findings and determine eligibility.
 
If any of these slit lamp findings are grade 3 or higher (FDA scale), the subject may not continue at this time, but may return up to one additional time to determine eligibility. If discontinued a final examination must be completed.
 
Limbal and Bulbar Conjunctival Hyperemia findings (████████) and Corneal Staining Assessment (████████) will also be collected for internal purposes.
 
If the clearance of the fluorescein needs to be expedited, preservative-free rewetting drops or saline may be instilled.

1.12	Keratometry	Record the keratometry readings OD and OS in diopters. This can come from any appropriate instrument so long as the same instrument is used at the Final Evaluation.
1.13	Iris Color	The investigator will record the subject's iris color based on the scale provided.
1.14	Subjective Spherocylindrical Refraction	Complete subjective spherocylindrical refraction and record the resultant distance visual acuity (OD, OS, and OU) to the nearest letter.
1.15	Eligibility after Baseline	
All responses to Inclusion Criteria questions must be answered "yes" and all responses to Exclusion Criteria questions must be answered "no" for the subject to be considered eligible.
 
If subject is deemed to be ineligible after baseline, proceed to Final Evaluation and complete Subject Disposition. Refraction and Biomicroscopy forms do not need to be completed as part of Final Evaluation.

**Clinical Study Protocol**  
**Johnson & Johnson Vision Care, Inc.**

Visit 1: Treatment 1 Lens Fitting		
Step	Procedure	Details
1.16	Lens Selection	
Assign the study lens based on the randomization scheme provided by the biostatistician.
 
Select the contact lens power based on the spherical equivalent from the subjective spherocylindrical refraction.
 
Record the test condition.

1.17	Lens Insertion	
The Investigator or the subject inserts the study lenses. Record the time of lens insertion.
 
Check for lens damage under the slit lamp before proceeding with lens settling.
 
Replace damaged lenses if applicable.
 
Ensure the subject is given a Patient Instruction Guide.

1.18	Lens Settling	Allow the study lenses to settle for a minimum of 5 minutes.
1.19	Subjective Best Sphere Over Refraction	Perform subjective best sphere refraction over the study lenses with a phoropter (adopt the maximum plus to maximum visual acuity (MPMVA) approach and record the best corrected distance visual acuity to the nearest letter (OD and OS).
1.20	Lens Power Modification (if applicable)	
Adjust the lens power if the subject's best sphere over-refraction is not plano.
 
For each power modification, select the adjusted fitting lens power as appropriate and repeat steps 1.17 through 1.19.
 
One power modification is allowed.

1.21	Subject Reported Ocular Symptoms	Subjects will respond to a verbal open-ended symptoms questionnaire.

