##### Inclusion Criteria after Screening

The subject must:

1. Read, understand, and sign the STATEMENT OF INFORMED CONSENT and receive a fully executed copy of the form.
2. Appear able and willing to adhere to the instructions set forth in this clinical protocol.
3. Be between 18 and 39 (inclusive) years of age at the time of screening.
4. By self-report, habitually wear spherical silicone hydrogel soft contact lenses in both eyes in a daily reusable or daily disposable wear modality (i.e. not extended wear modality). Habitual wear is defined as a minimum of 6 hours of wear per day, for a minimum of 5 days per week during the past 30 days.
5. Have a habitual contact lens prescription that is current within the prior 6 months, and they must have worn that prescription for at least 2 weeks prior to entering the study.

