**Clinical Study Protocol**  
**Johnson & Johnson Vision Care, Inc.**

Visit 1: Treatment 1 Lens Fitting		
Step	Procedure	Details
1.26	Dispense	
The lenses will be dispensed for 13-15 days
 
 
1. The subjects should wear their lenses similar to the inclusion criteria: <math>\geq 6</math> hours per day, <math>\geq 5</math> days per week.
 
2. The lenses will be worn as daily wear daily disposable only.
 
3. All subjects will be provided a bottle of ACUVUE RevitaLens to return any problematic lenses to the investigational site.
 
4. Rewetting drops are permitted if needed.
 
5. A patient instruction booklet will be provided.
 
 
Note 1: Ensure that the subject has enough lenses to last them to their next scheduled visit with no extras. In the event a lens is lost or damaged, and the subject has run out of lenses, the subject will return to the investigator site for replacement.
 
Note 2: The subject's habitual contact lenses cannot be worn at any time during the study.
 
Note 3: Remind the subjects to bring back any unworn lenses to the next visit.
 
Note 4: Remind the subject to bring a habitual form of correction to next visit.

1.27	Schedule next visit	
Schedule the follow-up visit to occur in <math>14 \pm 1</math> days (counting the day of this visit as day 0, the subject may return on day 13 through 15).

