# Clinical Study Protocol

## Johnson & Johnson Vision Care, Inc.

### VISIT 2

The follow-up will occur 13-15 days after Visit 1. The subjects must enter the visit wearing their study contact lenses.

Visit 2: Treatment 1 Follow-Up 1															
Step	Procedure	Details													
2.1	Adverse Events and Concomitant Medications Review	Review any changes to the subject's medical history or concomitant medications from the previous study visit. Record any changes, and any adverse events.													
2.2	Wearing Time	Record the average wearing time and comfortable wearing time.													
2.3	Compliance	Confirm compliance with the prescribed wear schedule.													
2.4	Return unworn lenses	Collect any unworn study lenses from the subject.													
2.5	Subject Reported Ocular Symptoms	Subjects will respond to a verbal open-ended symptoms questionnaire.													
2.6	Follow-Up Questionnaire	Subjects will respond to the following questionnaires: 1. CLUE Follow-up 2. GSI Product Performance 3. Lens preference to habitual													
2.7	Distance ETDRS LogMAR Visual Acuity	
Measure monocular distance high luminance high contrast (HLHC) visual acuity using ETDRS charts at 4 meters.
 
Measure each eye once using the charts shown in the table below:
 
  
 Condition	HLHC	
   
 Room illumination	> 400 lux	
 
 Chart luminance	120 - 200 cd/m^2	
 
 Eye	OD	OS	
 
 Charts	HC-1	HC-2	
  
 
Recorded letter-by-letter results into EDC.
	Condition	HLHC	Room illumination	> 400 lux	Chart luminance	120 - 200 cd/m 	Eye	OD	OS	Charts	HC-1	HC-2	
Condition	HLHC														
Room illumination	> 400 lux														
Chart luminance	120 - 200 cd/m 														
Eye	OD	OS													
Charts	HC-1	HC-2													
2.8	Visual Acuity	Record the distance Snellen visual acuity with the contact lenses (OD, OS, and OU) to the nearest letter. Subjects must read the smallest line until at least 50% of the letters are read incorrectly.													

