### Hypothesis Testing

The null and alternative hypotheses for testing superiority of the Test lens relative to the Control lens are as follows:

$$H_0: PR \leq 1.0$$
$$H_A: PR > 1.0$$

Where PR represents the preference ratio of Test lens to Habitual lens (proportion of subjects preferring Test to proportion of subjects preferring Habitual lens) at the 2-week follow-up. Superiority will be declared if the lower bound of the 2-sided 95% confidence interval is above 1.0.

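### The one-arm digital-devices preference test shows preference for a newly fitted study lens over the habitual lens; on its own it cannot be credited to the Test lens or its filter, and 14.6 wrongly presents it as superiority to Control.

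*Combined protocol and SAP*

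**What the plan says.** **Study lens (protocol 7.2, Visit 1).** A subjective refraction is done at step 1.14. Step 1.16 then instructs: "Select the contact lens power based on the spherical equivalent from the subjective spherocylindrical refraction". After settling and an over-refraction (step 1.19), step 1.20 says "Adjust the lens power if the subject's best sphere over-refraction is not plano", with one modification allowed. Both arms go through these steps.

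**Habitual lens.** Inclusion criterion 5 (3.2) requires the subject to "Have a habitual contact lens prescription that is current within the prior 6 months" and to have worn it for at least 2 weeks. At step 1.6 the investigator confirms both, the first as "The subject is wearing a SCL Rx that has been confirmed current (up-to-date) within the prior 6 months". Acuity in the habitual lenses is recorded at step 1.9, but no step over-refracts or updates them. From dispensing, "The subject's habitual contact lenses cannot be worn at any time during the study" (step 1.26, Note 2).

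**The item.** At Visit 2, step 2.6 gives every subject, with no restriction by arm, the questionnaire "Lens preference to habitual". The responses name the habitual and the study lenses (2.2).

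**The analysis.** In 14.6, "PR represents the preference ratio of Test lens to Habitual lens". The model uses Test-arm responses only, in three categories, with site as a random effect and gender, habitual lens type and iris category as possible covariates. Superiority is declared if the lower 95% limit for PR exceeds 1. The sentence introducing these hypotheses names the Control lens as comparator. Section 2.3 uses a phrase that merges Control and habitual.

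**The concern.** PR = 1 corresponds to no lens advantage only if everything else that differs between the study and habitual lenses has no net effect on preference. Four things differ besides the lens:

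- **Power.** The study lens is fitted to that day's refraction; the habitual lens is not re-checked.
- **Modality.** About 30% of subjects (about 43 of 143 completers per arm, Table 1) move from reusable to daily disposable lenses.
- **Awareness.** Over-labelling hides which study lens was assigned, but the subject always knows which lens is the habitual one.
- **Recall.** The habitual lenses have not been worn for about two weeks when the question is asked.

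The Control arm shares all four. By Table 3, Control has the same nominal specification as Test apart from the filter, so its answers would show how much preference arises without the filter. They are collected but not used in the planned test. At stake is the meaning of a positive result: a reader of 14.6 could take it as superiority over Control, or as an effect of the filter, when it shows neither.

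**Working it through.** **Inputs.** n = 143 Test-arm completers; assumed shares 0.40 prefer Test, 0.40 no preference, 0.20 prefer habitual; stated power 88% (14.2, Table 12). Decision rule: lower limit of the 2-sided 95% CI for PR above 1 (14.6). Shares below are written study/none/habitual.

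**Formula.** Without site or covariates, the generalized-logit estimate is ln PR = ln(n_T/n_H), with SE = √(1/n_T + 1/n_H). Superiority is declared if ln PR − 1.96·SE > 0.

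**The plan's figure.** Expected counts are 143 × 0.40 = 57.2 and 143 × 0.20 = 28.6. Then ln 2 = 0.693, SE = √(1/57.2 + 1/28.6) = 0.229, and the normal approximation gives Φ(0.693/0.229 − 1.96) = 85.7%. Multinomial simulation (400,000 trials) gives 87.8%, so the stated 88% reproduces.

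**No Test-lens effect, other factors moving preference.** The documents give no size for this, so the shifts are assumptions. The starting point is 30/40/30. A gain for the study lens can come from the no-preference group or from those preferring habitual, and the source matters.

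| Scenario | Shares | Superiority declared |
|---|---|---|
| No net effect | 30/40/30 | 2.4% |
| +3 points, from no preference | 33/37/30 | 6.3% |
| +3 points, from habitual | 33/40/27 | 15% |
| +6 points, from no preference | 36/34/30 | 14% |
| +6 points, from habitual | 36/40/24 | 45% |
| Familiarity favours habitual by 3 | 27/40/33 | 0.2% |

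**Using the Control arm.** The log ratio of the two PRs has SE = √(1/n_T + 1/n_H + 1/c_T + 1/c_H), where c_T and c_H are the Control-arm counts preferring the study and habitual lens. With 143 per arm and both arms at 40/40/20, the lower limit exceeds 1 in 2.4% of trials, so a shared refit effect cancels. With Test at 40/40/20 (PR = 2.0):

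| Control shares | Control PR | Ratio | SE (log) | 95% CI at expected counts | Power |
|---|---|---|---|---|---|
| 30/40/30 | 1.00 | 2.00 | 0.315 | 1.08 to 3.71 | 60% |
| 33/40/27 | 1.22 | 1.64 | 0.315 | 0.88 to 3.04 | 34% |
| 36/40/24 | 1.50 | 1.33 | 0.318 | 0.72 to 2.49 | 14% |

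For the first row, 1/57.2 + 1/28.6 + 1/42.9 + 1/42.9 = 0.0991, whose square root is 0.315, and 2.00 × exp(±1.96 × 0.315) gives the interval.

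**The case against.** The strongest objection is that nothing is wrong with the test. Section 14.6 defines PR as Test against habitual. If refitted subjects do prefer the study lens, PR exceeds 1 and rejection is correct. The secondary objective concerns market preference, for which the wearer's current lens is a natural comparator, daily replacement is part of the product, and awareness of one's own lens is unavoidable. This stands. A reader might infer that the percentages above are inflated type I error against a nominal 2.5%. They are not: they say how often a true preference over habitual would be wrongly credited to the lens.

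The direction is not established either. Subjects are established wearers of their own lenses (at least 6 hours a day, 5 days a week, criterion 4), so familiarity could push PR below 1. Criterion 5 and step 1.6 are real controls: they limit a power difference, though they require neither a plano over-refraction nor equal power. Habitual lens type is a stratification factor (5.1) and a possible covariate. A covariate in a one-arm model still cannot separate the lens from the refit.

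It is also tempting to read 88% as the rate of unearned claims. The 40/40/20 split is the plan's assumption for the Test lens, based on earlier Test-lens data. Nothing in the documents suggests that refitting alone would produce it.

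Finally, section 14.1 promises summary tables for efficacy variables and a stand-alone SAP that was not available here. Control responses may therefore be tabulated, and their absence is established only for the planned inferential model.

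What the objection leaves untouched is the Control wording in 14.6 and the absence of a planned between-arm estimate for this item.

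**Conclusion.** The point holds as a limit on interpretation. A PR significantly above 1 supports preference for the fitted Test lens over the habitual lens. It does not by itself support a claim over the Control lens or for the filter, and the introduction to the hypotheses in 14.6 misstates the comparator.

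With no Test-lens effect, the illustrations run from 0.2% (27/40/33) through 6-15% (3-point gain) to 14-45% (6-point gain). They rest on assumed shifts around 30/40/30, n = 143, and a model without site or covariates. The documents give neither the size nor the sign of the net refit, novelty and familiarity effect, so they do not support saying that the result will be biased towards the Test lens.

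The scope is one secondary endpoint. Study success depends on the primary hypotheses (2.3). The randomised Test-Control comparisons (acuity, CLUE scores, indoor clarity, fit, slit lamp) are not biased by the refit, because both arms receive it.

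**What to change.** - Keep the Test-versus-habitual test and its 88% power. Word its conclusion as preference for the fitted Test lens over the habitual lens.
- Correct the comparator in the 14.6 hypotheses, and align hypothesis 4 in 2.3 with it.
- Fit the same generalized-logit model to both arms with a lens term. Report the Control-arm PR beside the Test-arm PR, and their ratio with a 95% CI, as a supportive analysis.
- State that no claim over the Control lens or for the filter will rest on the one-arm test alone.

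The cost is text in 14.6, 2.3 and the stand-alone SAP, which 14.1 says will be finalised before database lock. The data are already collected. The downside is imprecision: power for the ratio falls from 60% to 34% or 14% as Control moves from 30/40/30 to 33/40/27 or 36/40/24. The ratio should therefore be reported as an estimate and not used as a success gate.
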